2.3 Exploratory Objectives

Table 2.3-1 Exploratory Objectives and Associated Endpoints

Type	Objective	Endpoint
Safety	To assess gastrointestinal tolerability across different titration schedules (Cohorts 1 and 2)	
 Percentage of subjects with gastrointestinal AEs at each dose level Percentage of subjects with nausea and vomiting from baseline (Day 1) over 7 days of treatment
PD	To assess the effect of MEDI0382 on glucose lowering during different meals and times of the day as measured by continuous glucose monitoring (CGM) (Cohort 1 only)	
 Change in percentage of time in hyperglycaemia (defined as > 7.8 mmol/l or > 140 mg/dl) and hypoglycaemia (defined as < 3 mmol/l or < 54 mg/dl) from baseline (Day -1) over 24 hours to the end of dosing at each dose level (Days 7, 14, 21, 28, and 49) Change in percentage of time in hyperglycaemia (defined as > 7.8 mmol/l or > 140 mg/dl) and hypoglycaemia (defined as < 3 mmol/l or < 54 mg/dl) over 7 days at each dose level (Days 1 to 7, Days 8 to 14, Days 15 to 21, and Days 22 to 28) Change in glucose AUC_{120min} during a standardised meal in the morning from baseline (Day -1) and at the end of 49 days of treatment Change in glucose AUC_{120min} during a standardised meal in the evening from baseline (Day -1) and at the end of 49 days of treatment
Efficacy	To characterise the effect of MEDI0382 on glucose lowering and weight versus placebo after 7, 14 and 49 days (Cohort 2 only)	
 Percentage change in glucose AUC as measured by a standardised MMTT from baseline (Day -1) after 14 and 49 days Change in fasting plasma glucose from baseline (Day -1) to the end of 7, 14, and 49 days of treatment Percentage and absolute change in body weight from baseline (Day 1) to the end of 7, 14, and 49 days of treatment Change in HbA1c from baseline (Day -1) to the end of 49 days of treatment

Table 2.3-1 Exploratory Objectives and Associated Endpoints

Type	Objective	Endpoint
PD	To assess the effect of MEDI0382 on ketone bodies, amino acids, and free fatty acid (FFA) levels over 49 days of treatment (Cohort 1 only)	
 Change in plasma beta-hydroxybutyrate from baseline (Day -1) while fasted and at 4 hours postdose after 49 days Change in FFA levels from baseline (Day -1) after 49 days of treatment Change in amino acid levels from baseline (Day -1) after 49 days of treatment
PD	To assess the effect of MEDI0382 on uric acid	
 Change in uric acid levels from baseline (Day -1) after 49 days of treatment

AE = adverse event; AUC = area under the concentration–time curve; CGM = continuous glucose monitoring; FFA = free fatty acids; GLP-1 = glucagon-like peptide-1; HbA1c = glycated haemoglobin; MMTT = mixed-meal tolerance test; PD = pharmacodynamics; T_{lag} = lag phase; T_{1/2} = half -life

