3.1.2 Treatment Regimen

MEDI0382 or placebo will be administered once daily via SC injection.

Cohort 1

- MEDI0382 50 µg for 7 days, followed by 100 µg for 7 days, followed by 200 µg for 7 days, and 300 µg SC once daily for 28 days (n = 26)
- Matched placebo SC once daily for 49 days (n = 13)

Cohort 2

- MEDI0382 50 µg for 14 days, followed by 100 µg for 14 days, followed by 200 µg for 14 days, and 300 µg SC once daily for 7 days (n = 18)
- Matched placebo SC once daily for 49 days (n = 6)

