3.2.3.3 Exploratory Endpoints

GLP-1 analogues are established to cause increased GI side-effects which are most pronounced in the early phases of treatment (Meier, 2012). The mechanisms underlying these symptoms are multifactorial and related to PK and effects on [REDACTED] and vomiting centers of the brain (area postrema) (Orskov et al, 1996). An added dimension of complexity here is that tolerance to the effects of GLP-1 receptor agonism on [REDACTED] may develop with short-term treatment (Nauck et al, 2011). In attempts to improve GI tolerability in this drug class, both dose up-titration (Victoza, 2014) and lengthening of titration intervals from between 1 to 4 weeks have been utilised (Exenatide, 2016). In a prior Phase 1/2 study (Study D5670C00002), subjects dosed with MEDI0382 titrated in 4-day intervals from 100 µg up to 200 µg across 41 days reported mild to moderate nausea (13/25, 52%) and vomiting (8/25, 32%); however, the number of nausea and vomiting events diminished in frequency with dose up-titration (n = 19 at 100 µg, n = 10 at 150 µg, and n = 11 at 200 µg) and in most cases, events were noted to occur within 3 days of a dose up-titration step. In Cohorts 5 and 6 of Study D5670C00002, a comparison of different dose up-titration steps was made: 100 µg → 150 µg → 200 µg → 300 µg (Cohort 5; n = 11) versus 100 µg → 200 µg → 300 µg (Cohort 6; n = 12) with 5-day up-titration steps in between. The percentage of subjects reporting nausea was lower with an intermediate 150 µg dose up-titration step between 100 and 200 µg (27% vs 42%); however, the percentage of subjects with vomiting was in fact higher in this group (27% vs 8%). These results and the prior clinical experience with GLP-1 analogues imply that further modulation of the titration schedule may help to minimise GI side-effects experienced with MEDI0382. To investigate different titration schedules, Cohort 1 of this study will test a lower starting dose of MEDI0382 (50 µg) than has been previously tested in overweight and obese subjects with T2DM, and with longer up-titration steps (7 days). Cohort 2 will run in parallel with Cohort 1

and will test up-titration of MEDI0382 every 2 weeks in order to assess if this further minimises GI AEs.

[REDACTED]

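### The dose-level GI percentages used to compare titration schedules partly reflect unequal days at each level; the distortion is probably modest, and a 7-day window after each step would equalise time at risk

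*Protocol*

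**What the plan says.** Protocol Table 2.3-1 sets the exploratory objective "To assess gastrointestinal tolerability across different titration schedules (Cohorts 1 and 2" and lists two endpoints under it. The first is "Percentage of subjects with gastrointestinal AEs at each dose level". The second is nausea and vomiting over the first 7 days of treatment.

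Protocol 3.2.3.3 explains the slower schedule: Cohort 2 "will test up-titration of MEDI0382 every 2 weeks in order to assess if this further minimises GI AEs". Section 1.5 lists this question among the three reasons for the study.

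Protocol 3.1.2 fixes the schedules. In Cohort 1 the 50 and 100 µg levels last a week each, and the rest of the schedule reads "followed by 200 µg for 7 days, and 300 µg SC once daily for 28 days (n = 26". Cohort 2 takes 50, 100 and 200 µg for 14 days each, and its 300 µg period is "SC once daily for 7 days (n = 18".

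Protocol 4.8.4 and SAP 3.6.1 both count a subject once per type of event. The readable text gives no fixed window per dose level, no exposure adjustment and no rule assigning an event to a level. SAP 3.6.1 ends in a blacked-out block, so such a rule could sit there.

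On timing in the earlier multiple-dose study, Protocol 3.2.3.3 says that, in the main, "events were noted to occur within 3 days of a dose up-titration step".

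**The concern.** A once-per-subject percentage can only rise as the window lengthens. If two schedules are equally tolerable but one keeps subjects at a level longer, that schedule will tend to show more subjects with an event at that level. Here the imbalance changes direction. The crude figures tend to count against the slower schedule at 50, 100 and 200 µg and in its favour at 300 µg.

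A reader of the dose-level table could then conclude that slower titration helps at the top dose, or hurts at the lower doses, when part of the difference is days at risk. The other endpoint under the objective does not settle the matter: during Days 1 to 7 both cohorts take 50 µg, so their dosing is identical.

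**Working it through.** **Inputs.** Days at each level: Protocol 3.1.2. Earlier incidence over 41 days: nausea 13/25 (52%) and vomiting 8/25 (32%), Protocol 3.2.3.3. Earlier event counts: 19, 10 and 11 at 100, 150 and 200 µg (Protocol 1.4 calls them vomiting; 3.2.3.3 calls them nausea and vomiting; this does not change the argument).

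**Step 1: the plan's own total.** Cohort 1: 7 + 7 + 7 + 28 = 49 days. Cohort 2: 14 + 14 + 14 + 7 = 49 days. Both match the stated 49 days.

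**Step 2: time at risk by level.**

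| Level | Cohort 1 | Cohort 2 | Longer/shorter |
|---|---|---|---|
| 50, 100, 200 µg (each) | 7 d | 14 d | 2.0 |
| 300 µg | 28 d | 7 d | 4.0 |

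**Step 3: constant hazard, as an upper illustration.** Take h = −ln(1 − p)/41 and P(d) = 1 − exp(−h·d), the same in both cohorts.

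| Basis | h per day | 7 d | 14 d | 28 d | 14 v 7 | 28 v 7 |
|---|---|---|---|---|---|---|
| Nausea 52% | 0.0179 | 11.8% | 22.2% | 39.4% | 1.9 | 3.3 |
| Vomiting 32% | 0.0094 | 6.4% | 12.3% | 23.2% | 1.9 | 3.6 |

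**Step 4: is a constant hazard plausible?** Reading Protocol 1.4 as 4 days at 100 µg, 4 at 150 µg and 41 − 4 − 4 = 33 at 200 µg (the 33 is inferred), events per day were 19/4 = 4.75, 10/4 = 2.5 and 11/33 = 0.33. Risk fell steeply, which agrees with the protocol's remark about the first 3 days after a step.

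**Step 5: front-loaded risk.** Let p3 be the risk in the first 3 days after a step and b a daily background hazard afterwards. P(d) = 1 − exp(−[−ln(1 − p3) + b·(d − 3)]). Both parameters are assumptions. The top value of b is 11/(25 × 33) = 0.0133.

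| p3 | b | 7 d | 14 d | 28 d | 14 v 7 | 28 v 7 |
|---|---|---|---|---|---|---|
| 10% | 0 | 10.0% | 10.0% | 10.0% | 1.00 | 1.00 |
| 10% | 0.005 | 11.8% | 14.8% | 20.6% | 1.26 | 1.75 |
| 10% | 0.0133 | 14.7% | 22.2% | 35.5% | 1.52 | 2.42 |
| 20% | 0.005 | 21.6% | 24.3% | 29.4% | 1.12 | 1.36 |
| 20% | 0.0133 | 24.1% | 30.9% | 42.6% | 1.28 | 1.77 |
| 30% | 0.005 | 31.4% | 33.7% | 38.2% | 1.08 | 1.22 |
| 30% | 0.0133 | 33.6% | 39.5% | 49.8% | 1.18 | 1.48 |

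With b = 0 the ratios are 1.0 whatever p3 is. In this model the distortion disappears only if no further subject has a first event after day 3.

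**Step 6: would a rate per subject-week do better?** Suppose 20% of subjects have one event just after the 300 µg step in each cohort and none later. The rates are 0.20/4 = 0.05 per week in Cohort 1 and 0.20/1 = 0.20 per week in Cohort 2. That is a spurious four-fold difference the other way.

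**The case against.** **The timing of events limits the effect.** A reader might infer from the four-fold difference in days that the 300 µg percentages are distorted three- or four-fold. The documents do not support that. It needs a constant hazard, and the protocol's own experience is of events clustered after steps. This stands, and the front-loaded range is the fairer guide.

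**An equal-length comparison is already planned.** A reader might also infer that the plan has no fair way to compare the schedules. SAP 3.6.1 summarises treatment-emergent AEs by system organ class, by treatment group for each cohort. The GI row is therefore a whole-study percentage by cohort, over 49 days of dosing in each, and Protocol 5.4.1 ends AE collection at the same post-dose visit window in both. This largely stands. That summary equalises duration but not the mix of doses, and it says nothing about individual levels, which is what the listed endpoint is for.

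**Within a cohort the contrast is balanced.** Active and placebo subjects share the same calendar periods, so the randomised comparison has equal days at risk. Randomisation is to treatment within each cohort (Protocol 4.6.1), and a footnote to Table 4.2.1-1 lets reluctance to wear a CGM device steer a subject to Cohort 2. No readable text specifies a between-cohort test of this endpoint. All true; the cross-cohort reading is descriptive with or without a fixed window.

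**Noise is large.** In the most distorted front-loaded case at 300 µg, 35.5% of 26 v 14.7% of 18 differ by 20.8 points. The 95% half-width is 1.96 × √(0.355 × 0.645/26 + 0.147 × 0.853/18), about 25 points. This supports a low severity, but noise does not cancel a systematic shift.

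**Redaction.** It cannot be claimed that the SAP lacks a dose-level rule, because one may be in the blacked-out text.

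**Conclusion.** The point holds in a limited form. As Protocol Table 2.3-1 defines it, the dose-level GI percentage mixes tolerability with days at risk when the cohorts are compared. Time at risk is two-fold longer in Cohort 2 at 50, 100 and 200 µg and four-fold longer in Cohort 1 at 300 µg. The day counts are exact; their effect on the percentages is not known. Under assumed front-loaded risk (p3 of 10 to 30%, background 0 to 0.0133 per day, no true schedule effect) the ratio is about 1.0 to 2.4 at 300 µg and 1.0 to 1.5 at the lower levels. The constant-hazard ratios of 3.3 to 3.6 and about 1.9 are an upper illustration. They use nausea and vomiting separately, since the documents give no earlier figure for any GI AE.

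The endpoint is exploratory, the arms are small, and a whole-study summary by cohort exists. This is therefore an improvement worth considering, not a flaw that undermines the trial.

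**What to change.** For the between-cohort comparison, report the percentage of subjects with GI AE onset in the first 7 days after starting each dose level. These are Days 1–7, 8–14, 15–21 and 22–28 in Cohort 1, and Days 1–7, 15–21, 29–35 and 43–49 in Cohort 2. Every level lasts at least 7 days in both cohorts, so the ratio of time at risk becomes 1.0 throughout. Table 2.3-1 and SAP 3.5.1.1 already use the same Cohort 1 windows for the 7-day CGM measures.

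Keep the crude dose-level percentages, with days at each level beside them, and read both with the planned whole-study GI percentage by cohort. Do not use a rate per subject-week for this comparison: it dilutes front-loaded events in the longer period. State that the cross-cohort comparison is descriptive.

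The cost is a sentence of wording and one variable derived from AE onset dates. If the redacted SAP text already sets such a window, only the protocol wording needs aligning. The downside is that events after the first week at a level appear only in the crude and whole-study summaries. Given the reported clustering after steps, little should be lost.

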3 STUDY DESIGN

3.1 Description of the Study

3.1.1 Overview

This is a randomised, double-blind, placebo-controlled study to evaluate the efficacy, safety, tolerability, and PK profile of 50 and 300 µg of MEDI0382 in overweight and obese subjects with T2DM. Up to 63 subjects are planned to be enrolled across multiple study sites.

The study is divided into 2 cohorts that will be recruited in parallel; for both cohorts, subjects will be consented, screened for suitability, and randomised within 60 days if eligible. A total of 39 subjects will be randomised to Cohort 1, and 24 subjects will be randomised to Cohort 2. Cohort 1 will evaluate the efficacy, safety, tolerability, and PK of MEDI0382 when titrated up in weekly intervals from 50 to 300 µg and administered over 49 days. Cohort 2 will explore an alternative 2-week titration schedule, and will provide additional information on the PK profile and glucose-lowering efficacy of 50 µg MEDI0382

Cohort 1

Subjects will undergo safety blood tests at any time from Day -7 to Day -3 if the screening visit is more than 7 days before Day 1. On Day -2, subjects will be admitted to the clinical unit for 2 nights and will undergo further initial safety assessments and training in SC injection administration; normal saline will be used for SC injection administration training. At this time an ambulatory blood pressure monitoring (ABPM) device will be fitted on Day -2 and worn for 24 hours; simultaneously a continuous glucose monitoring (CGM) device will be fitted on the contralateral arm and the subject will be given training for CGM use (Figure 3.1.1-1). Subjects will be expected to wear the CGM continuously until the end of dosing. On Day -1, eligibility criteria will be verified and subjects will undergo 2 mixed-meal tolerance test (MMTT) assessments (Meal type A; with serial blood sampling in the morning, and meal type C without serial blood sampling on the evening of that day). Subjects can be randomised after confirming eligibility at any time from Day -1 to Day 1 (predose) to receive either MEDI0382 or placebo. On Day 1, dosing will commence following predose safety measures including vital signs, blood tests for safety, glycated haemoglobin (HbA1c) and exploratory biomarkers, an ECG, and measurement of weight. Since the dose of 50 µg will require a dilution by site staff prior to administration, subjects will have the option to remain as an inpatient or alternatively attend the clinical unit every day for dosing during the first week; during this time subjects will undergo supervision to self-administer the investigational product. On Day 7, safety assessments will be performed and the MMTT meal type B, with serial blood sampling, will be repeated; where relevant, subjects will be discharged home (refer to Section 4.3.1.1 for description of MMTT meal types).

Subjects will then return to the clinical unit at weekly intervals until a maintenance dose of 300 µg is achieved. On Day 22, subjects will be readmitted to the clinical unit for an overnight stay to undergo PK sampling and ABPM for 24 hours. Subjects will be discharged on Day 23 and will thereafter attend for weekly visits for safety assessments and ABPM application. At the end of dosing, subjects will be readmitted to the clinical unit for a final overnight stay, and an MMTT (Type A) will be repeated alongside safety assessments, ABPM, measurement of weight, and blood tests. A second MMTT (Type C) without serial blood sampling will be performed on the evening of Day 49 and an HbA1c and exploratory biomarkers will be repeated. A 7- to 14-day post-last dose follow-up visit and final follow-up visit approximately 28 days after the last dose will be performed for safety assessments, and a final ABPM recording will be made at this time.

Cohort 2

Study procedures for Cohort 2 will be similar to Cohort 1 at baseline, although subjects will not undergo ABPM assessments nor wear a CGM monitor in this cohort. [REDACTED]

[REDACTED]
[REDACTED]
[REDACTED] Safety bloods will be performed at anytime from Day -7 to Day -3 if the screening visit was more than 7 days before Day 1 (Figure 3.1.1-1). Subjects may be confined to rest for the duration of the breath test period. On admission to the clinical unit on Day -2, subjects will undergo further baseline safety assessments and undergo their first MMTT (Type A) with serial blood sampling on Day -1. Dosing will commence on Day 1. Since the dose of 50 µg will require a dilution by site staff prior to administration, subjects will be given the option to either remain as an inpatient, or attend the clinical unit every day during the first 2 weeks of dosing, but will be required to stay overnight for a total of 5 nights across this period (on Days -2, -1, 1, 7, and 14); thereafter, subjects will attend the unit for dose up-titration. During this time subjects will self-administer investigational product under supervision. [REDACTED] and MMTTs (Type B) with serial blood sampling will be repeated at different points across the study as described in the schedule. At the end of dosing on Day 49, subjects will be admitted for a final overnight stay; a repeat MMTT (Type A) will be performed, alongside measurement of weight and safety assessments. [REDACTED]

[REDACTED] A 7- to 14-day post-last dose follow-up visit and final follow-up visit approximately 28 days after the last dose will be performed for safety assessments [REDACTED]
[REDACTED]

[figure not shown]

Figure 3.1.1-1 Study Flow Diagram

ABPM = 24-hour ambulatory blood pressure (and heart rate) monitoring; AUC = area under the concentration-time curve; CGM = continuous glucose monitoring; Coh = cohort; [REDACTED]
 MMTT = mixed-meal tolerance test; n = number of subjects; V = visit

Assessments detailed in the schematics illustrate that those assessments will occur at that particular visit (unless specified otherwise), but they will not necessarily occur on the same day.

There is also a post-last dose visit 7 to 14 days after the last dose (Visit 10 for Cohort 1 and Visit 8 for Cohort 2), and there is a final follow-up visit (Visit 11 for Cohort 1 and Visit 9 for Cohort 2) approximately 28 days after the last dose for both cohorts.

The endpoints to be measured in this study are described in Section 2.

3.1.2 Treatment Regimen

MEDI0382 or placebo will be administered once daily via SC injection.

Cohort 1

- MEDI0382 50 µg for 7 days, followed by 100 µg for 7 days, followed by 200 µg for 7 days, and 300 µg SC once daily for 28 days (n = 26)
- Matched placebo SC once daily for 49 days (n = 13)

Cohort 2

- MEDI0382 50 µg for 14 days, followed by 100 µg for 14 days, followed by 200 µg for 14 days, and 300 µg SC once daily for 7 days (n = 18)
- Matched placebo SC once daily for 49 days (n = 6)

3.1.3 Dose Escalation

Doses will escalate from the initial dose of 50 µg to 300 µg in 1-week intervals for Cohort 1 and in 2-week intervals for Cohort 2 (Section 3.1.2).

3.1.4 Management of Study Medication Related Toxicities

3.1.4.1 Tolerability

If a subject experiences nausea and vomiting in relation to investigational product, in the first instance, conservative measures should be advised including reducing meal size and maintaining adequate hydration. Where necessary, if there is persistent vomiting a subject may be given an antiemetic to control his/her symptoms; a 5HT3 receptor antagonist (eg, ondansetron) or cyclizine is preferable in this situation, rather than antiemetics [REDACTED] and in particular dopamine receptor antagonists (eg, metoclopramide or domperidone).

3.1.4.2 Hypoglycaemia

A hypoglycaemic event is considered severe if associated with severe cognitive impairment requiring external assistance for recovery, as defined by the American Diabetes Association. Spontaneous and clinically significant hypoglycaemia defined as blood glucose < 3.0 mmol/L or 54 mg/dL with or without symptoms (Skyder et al, 2017) has not been experienced in prior studies with MEDI0382 up to a dose of 300 µg alongside metformin

treatment and is therefore unlikely to occur in this study. All subjects (both Cohorts 1 and 2) will be provided with a diary and a glucometer and will be advised to check their capillary blood glucose level if they have symptoms of hypoglycaemia (hunger, dizziness, shaking, sweating, or irritability) or feel unwell and will be expected to record the level in their diary. Local protocols for treatment and follow-up of any hypoglycaemic episode should be followed. Any blood glucose level of < 3.0 mmol/L (54 mg/dL) is considered as clinically important hypoglycaemia and should be reported by investigators as an AE. Pharmacological treatments administered for hypoglycaemia, eg, dextrose/glucose tablets, glucagon etc should be recorded in the electronic case report form (eCRF) as concomitant medications.

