3.2.3.2 Secondary Endpoints

Additional Measures of Glucose Lowering and Weight Loss

In order to better characterise the glucose-lowering efficacy of MEDI0382 up to 300 µg across 49 days of dosing, additional markers of glucose control including HbA1c and fasting glucose level will be measured, alongside exploratory measures of glucose control generated by CGM. Absolute change in weight will also be measured and the proportion of subjects achieving clinically significant weight loss (> 5% of body weight) will be recorded.

In evaluating the 50 µg dose of MEDI0382, this study will determine if repeat administration of 50 µg is more effective than placebo with respect to glucose lowering at 7 days through measurement of glucose AUC during a standardised MMTT. Results from the prior multiple-ascending-dose study (Study D5670C00002) of MEDI0382 on glucose AUC reduction have shown a reduction of 41.8% after 7 days at 100 µg, 36.7% after 11 days at 150 µg following up-titration from 100 µg, and 39.6% after 15 days at 200 µg following up-titration from 100 µg and 150 µg. Results from this previous study will be used as a benchmark to further evaluate the results.

Safety and Tolerability

In prior studies (Study D5670C00002), 300 µg of MEDI0382 has been administered to 23 obese and overweight subjects with T2DM for 7 days after 2 up-titration steps, and was shown to have an acceptable tolerability and safety profile over this period of dosing. During treatment, there was no significant increase in systolic or diastolic BP, but a significant increase in heart rate of 6.6 beats per minute (90% CI 4.1, 9.1) was recorded after 7 days of dosing (Cohorts 5 and 6 pooled data; n = 19). In the cohorts that received MEDI0382 up-titrated to 300 µg, nausea and vomiting were observed in a maximum of 41.7% (Cohort 6) and 27.3% (Cohort 5) of subjects, respectively. Safety and tolerability with greater exposure at the 300 µg dose level will be measured with safety laboratory tests, ABPM recording of heart rate and BP and other vital signs, and recording of AEs.

Pharmacokinetic Profile and Immunogenicity

Plasma concentrations of MEDI0382 at 50 and 300 µg will be used to evaluate the PK profile (C_{max} , time to maximum concentration [T_{max}], AUC_{tau} , and $C_{min}[R_0]$ [accumulation ratio]). In addition, C_{trough} at other dose levels will be evaluated to establish steady state achievement.

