4.3.3.1 Glucometer Measured Capillary Blood Glucose Readings

At the start of the study, each subject in both cohorts will be issued a standardised glucometer, testing strips, and a diary. Subjects will be encouraged to perform finger-prick tests if they feel unwell and in particular if they feel the symptoms may be due to hypoglycaemia for the duration of the study, but they will not be required to test routinely. If the investigator/site staff feel that a subject could be experiencing hypo- or hyperglycaemia, capillary blood glucose should be tested with a standardised glucometer. Capillary blood glucose levels of < 3 mmol/L (54 mg/dL) should be recorded as an AE regardless of whether the subject has symptoms or not.

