3.5.1.2 Analysis of Pharmacodynamic Endpoint(s)

All of the PD measures will be summarized by scheduled visits. Except for the analyses specified in the following of this section, all of the other PD endpoints will be analyzed for the end-of-treatment measure only using similar ANCOVA model as that in the primary analysis. Treatment effect and baseline value (if available) will be added in the model.

[REDACTED]

[REDACTED]

The CV of CGM glucose values over 7 days at each dose level will be analyzed with a 2-sample t-test (assuming equal variance).

The change in percentage of time in hyperglycemia and hypoglycemia over 24 hours from baseline (Day -1) to Day 49 will be analyzed with the Wilcoxon rank sum test.

The percentage of time in hyperglycemia and hypoglycemia over 7 days at each dose level will be analyzed with the Wilcoxon rank sum test.

The morning (type A) and evening (type C) MMTT CGM glucose AUC_{0-2hr} on baseline (Day -1) and Day 49, will be summarized. Their difference and agreement will be analyzed by the paired t-test and the concordance correlation coefficient, respectively. The CGM glucose AUC_{0-4hr} during MMTT on baseline (Day -1), Day 7, and Day 49, and the corresponding plasma glucose AUC_{0-4hr} will be summarized and analyzed in a similar manner.

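### Hypoglycaemia AEs rest largely on symptom-triggered tests, and the evenly sampled Cohort 1 CGM record yields no stated proportion of affected subjects and is not analysed for hypoglycaemia on Days 29-48

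*Protocol*

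**What the plan says.** **How a low value is found.** Protocol 3.1.4.2 says that a glucose below 3.0 mmol/L (54 mg/dL) "is considered as clinically important hypoglycaemia and should be reported by investigators as an AE". In both cohorts subjects are told to check capillary glucose "if they have symptoms of hypoglycaemia (hunger, dizziness, shaking, sweating, or irritability) or feel unwell and will be expected to record the level" in a diary. Protocol 4.3.3.1 encourages such tests "but they will not be required to test routinely"; site staff test when they suspect a problem. Blood glucose measured regardless of symptoms comes mainly from the meal tests, and the serum chemistry panel in Protocol 4.3.3 lists no glucose.

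**How often it is expected.** Protocol 3.1.4.2 says that spontaneous, clinically significant hypoglycaemia "has not been experienced in prior studies with MEDI0382 up to a dose of 300 µg alongside metformin", and judges it unlikely here.

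**Feeling unwell on the drug.** For the cohorts that reached 300 µg, Protocol 3.2.3.2 says "nausea and vomiting were observed in a maximum of 41.7% (Cohort 6) and 27.3% (Cohort 5) of subjects". Protocol 3.2.3.3 gives the detail: nausea in 27% and 42% and vomiting in 27% and 8% of Cohorts 5 and 6, against 52% and 32% in the cohort titrated from 100 to 200 µg.

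**CGM.** Only Cohort 1 wears it, with a reading every 15 minutes (Protocol 4.3.6.2). Sites are told to avoid looking at the readings unless an AE or SAE makes them useful.

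**Planned analyses.** SAP 3.6.1 tabulates AE incidence by preferred term, treatment group and cohort, counting each subject once. For CGM, SAP 3.5.1.2 summarises PD measures by scheduled visit. It applies a Wilcoxon test to the 24-hour change from Day -1 to Day 49 in percentage of time low, and adds: "The percentage of time in hyperglycemia and hypoglycemia over 7 days at each dose level will be analyzed with the Wilcoxon rank sum test". SAP 3.5.1.1 sets those windows at Days 1-7, 8-14, 15-21 and 22-28. The default level for these tests is two-sided 0.10 (SAP 3.1).

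**The concern.** A subject with nausea or vomiting has a protocol-given reason to measure glucose; a subject who feels well does not. If the drug makes more subjects feel unwell, more active subjects will look for low values, and the AE table could show more hypoglycaemia on MEDI0382 at the same true rate. CGM may be opened after an AE, which adds a second AE-driven route to detection.

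The CGM record in Cohort 1 does not depend on symptoms. As planned, it yields percentage-of-time summaries and rank tests. These do not state how many subjects had a clinically important low or how large that share could be, and most of the time at the final dose level is left out. Safety and tolerability is a secondary objective, and Protocol 3.2.3.1 says that 300 µg is being given for longer than before.

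**Working it through.** The documents state no rate, power or sample size for hypoglycaemia, so there is no plan figure to reproduce.

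**1. Prompting to test.** Nausea on drug is 27% to 52% (Protocol 3.2.3.3). Placebo nausea is not given; I assume 5%, 10% or 20%. The ratio of the shares prompted to test is:
- at 52% on drug: 0.52/0.05 = 10.4, 0.52/0.10 = 5.2, 0.52/0.20 = 2.6
- at 27% on drug: 0.27/0.05 = 5.4, 0.27/0.10 = 2.7, 0.27/0.20 = 1.35

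These are ratios of subjects with a reason to test, not of recorded events. The effect on AE counts cannot be computed from the documents.

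**2. Symptom-independent blood glucose.** Post-baseline meal tests give 2 days × 9 samples = 18 values per subject in Cohort 1 (Days 7 and 49) and 3 × 11 = 33 in Cohort 2 (Days 7, 14 and 49). All are taken in clinic, fasting or within 4 hours of the meal.

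**3. CGM coverage.** One reading per 15 minutes is 96 a day, so full wear over Days 1-49 gives 49 × 96 = 4,704 readings. The four windows use 28 × 96 = 2,688, and the last test uses Day 49. Days 29-48 (20 × 96 = 1,920 readings) are in neither. Dosing at 300 µg runs from Day 22 to Day 49, so 20 of its 28 days are missing.

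**4. What the rank test can show.** Inputs: 26 active and 13 placebo subjects (Protocol 4.1.1), all placebo values zero, k active values positive and distinct. Then U − mean = 6.5k. With t = 39 − k tied zeros, the variance is (26 × 13/12) × [40 − (t³ − t)/(39 × 38)].

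For k = 5: U − mean = 32.5, less 0.5 for continuity = 32. With t = 34, (t³ − t)/1482 = 39,270/1482 = 26.50. The variance is 28.17 × 13.50 = 380.3, SD 19.50, z = 1.641, p = 0.101.

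| k of 26 (placebo 0 of 13) | Wilcoxon p | Fisher p |
|---|---|---|
| 3 (12%) | 0.221 | 0.538 |
| 4 (15%) | 0.149 | 0.281 |
| 5 (19%) | 0.101 | 0.149 |
| 6 (23%) | 0.068 | 0.081 |
| 7 (27%) | 0.045 | 0.073 |

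With placebo at zero, both tests need k ≥ 6 for p < 0.10. Power is then P(Binomial(26, π) ≥ 6): 4% at π = 10%, 42% at 20% and 84% at 30%, the same for either test.

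**5. What estimation would show.** The upper limit of the exact 90% interval for 0 of n is 1 − 0.05^(1/n).
- 0 of 26: 1 − 0.05^(1/26) = 10.9%
- 0 of 23, the earlier 300 µg group treated for 7 days (Protocol 3.2.3.2): 12.2%
- 5 of 26 (19.2%), by Clopper-Pearson, with limits at the 0.05 quantile of Beta(5, 22) and the 0.95 quantile of Beta(6, 21): 7.9% to 36.3%

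**The case against.** Several objections are sound and limit the point.

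- **A reader might infer that the AE table gives no rate.** SAP 3.6.1 does give a subject-level incidence by arm. What it lacks is even ascertainment and an interval.
- **A reader might infer that Wilcoxon is the wrong test.** The table above shows that Fisher's test on the proportions is no more sensitive. The weakness comes from rarity and 26 v 13 subjects.
- **A reader might infer that CGM values will be almost all zero.** Protocol 3.1.4.2 speaks of blood glucose. No CGM rate is given, and interstitial readings may be low more often.
- **A reader might infer that AE bias against the drug is established.** The 52% and 32% come from a 100 µg start with 4-day steps. This trial starts at 50 µg with longer steps, chosen to reduce GI events. Without a placebo rate, uneven testing is plausible but not shown. If true lows are nearly absent, extra testing finds little. The two parts of the point matter most in different settings: uneven detection when lows occur, uninformative tests when they are rare.
- **CGM is not reduced to a rank test alone.** Summaries by visit include the maximum (SAP 3.1), which would reveal that at least one subject was affected in an analysed window, though not how many.
- **This is exploratory.** CGM hypoglycaemia is an exploratory endpoint in a phase 2a trial, and hypoglycaemia is not an AESI. Table templates sit in a separate programming plan, and parts of SAP 3.5.1.2 and 3.6.1 are redacted, so one can say only that no such output is stated.

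What remains after these objections is the symptom-triggered route to most AEs, the gap on Days 29-48, and the absence of a stated proportion with an interval from the one evenly sampled source.

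**Conclusion.** The point holds as a cheap improvement, not as a flaw that threatens a primary or secondary conclusion. AE-based hypoglycaemia may be unevenly ascertained between arms, in a direction that would count against the drug; its size is unknown because placebo nausea is not given. The Cohort 1 CGM record could supply an evenly ascertained estimate, but the stated analyses leave out 20 of the 28 days at 300 µg and give no proportion of affected subjects.

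If lows are rare, a non-significant rank test is compatible with up to 5 of 26 active subjects (19%) affected and none on placebo, and replacing the test would not help. An interval would: even zero affected subjects bounds the active-arm share at 10.9%. These figures assume 26 and 13 evaluable subjects, placebo values all zero, and the asymptotic Wilcoxon with tie and continuity correction.

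**What to change.** In SAP 3.5.1.2, for Cohort 1:

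- Add the number and percentage of subjects with CGM glucose below 3.0 mmol/L by arm, by dose level and over Days 1-49, with exact 90% intervals and an interval for the difference between arms.
- Pre-specify what counts, for example two consecutive readings below the threshold.
- Keep the Wilcoxon tests.

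In SAP 3.6.1, for both cohorts, label AE-based hypoglycaemia as largely symptom-triggered, and show by arm how many subjects recorded a capillary test in the diary.

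The cost is one extra CGM table from data already collected, plus diary counts. No procedure, dose or clinical rule changes. The downside is that some low sensor readings may be artefact, which a two-reading rule limits but does not remove. Cohort 2 has no CGM, so for its 24 subjects only the label and the test counts apply, and uneven ascertainment there is disclosed but not repaired.
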